9.2 Subject Accountability

The disposition of all enrolled subjects will be tabulated based on two migraine types (EM vs CM) separately and overall population using FAS.

The number and percentage of subjects who were enrolled, received investigational product, completed investigational product, discontinued investigational product and reasons for discontinuing, completed study, discontinued study and reasons for discontinuing will be summarized by the two migraine types (EM vs CM) separately, and the overall population. Summary of subjects who discontinue investigational product/study due to COVID-19 control measures will be included.

In addition, the descriptive summaries listed below will be done by the two migraine types (EM vs CM) separately and overall population using safety analysis set.

- At week 12, the number and percentage of subjects who remained on 70 mg and did not receive any 140 mg dose, who increased the dose to 140 mg, and who received 70 mg at week 12 and have received at least one dose of 140 mg previously.
- At week 12, the number and percentage of subjects who continued or discontinued SOC

The summary of the study reporting phase including a description of key dates such as the first subject enrolled, last subject enrolled, last subject's end of investigational product, last subject's end of study will also be provided using FAS by the two migraine types (EM vs CM) separately and overall population.

9.3 Important Protocol Deviations

Important Protocol Deviations (IPDs) categories are defined by the study team before the first subject's initial visit and updated during the IPD reviews throughout the study prior to database lock. These definitions of IPD categories, subcategory codes, and descriptions will be used during the course of the study. Eligibility deviations are defined in the protocol.

The final IPD list will be used to produce the Summary of IPDs table and the list of subjects with IPDs using the FAS.

Protocol deviations related to COVID-19 control measures will be summarized separately.

9.4 Demographic and Baseline Characteristics

Subject demographic and baseline disease characteristics will be summarized using descriptive statistics separately for the two migraine types and overall study population using FAS. If multiple races have been reported for a subject, the subject will be categorized as multiple race.

The following demographics and baseline disease characteristics will be summarized:

- Age
- Sex
- Ethnicity
- Race
- Height (cm)
- Weight (kg)
- Body Mass Index (BMI, kg/m²)
- Overall Migraine
- **Prior migraine preventive medication by categories**
- **Reasons for stopping of the prior migraine preventive medication by categories**
- **General medical history**
- **Type of SOC for dissatisfaction with SOC**
- Summary of prior migraine preventive medication and reasons for discontinuation
- **PRO (TSQM 1.4, MFIQ, MSSS, MIBS-4, GAD-7, PHQ-9, and ETS) at baseline**
- **Targeted neurological medical history**
- Disease duration of migraine
- Age at onset of migraine
- Monthly headache days during baseline period
- Monthly migraine days during baseline period
- Monthly acute migraine-specific medication days during baseline period

9.5 Efficacy Analyses

The final analysis of primary, secondary and exploratory endpoints will utilize the efficacy analysis set.

The primary and secondary endpoints will be analyzed in the following subgroups:

- Whether remained on standard of care migraine preventive treatment throughout the study (yes vs no)
- Migraine type (EM vs CM)

Detailed analysis methods and covariates included in the models are summarized in the table below. The value for the covariate “prevailing dose from week 12 onwards” will be the prevailing dose if all three planned doses are administered, or the last dose if two or fewer doses are administered from week 12 to week **20 or last observed dose prior to week 12 if none of three doses are administered**.

Table 9-1. Primary Efficacy Endpoint and analysis Summary Table

Endpoint	Primary Summary and Analysis Method
Change from baseline in the Treatment Satisfaction Questionnaire for Medication (TSQM) overall satisfaction scale score at week 24, as measured by items 12 to 14 of the TSQM version 1.4 (Note: Results from individual time point and mean over time points will also be generated in the same repeated measures mixed effects model.)	
1. Summary statistics using observed data (after intercurrent event handling)
 
2. The change from baseline in the TSQM overall satisfaction scale score at week 24, as measured by items 12 to 14 of the TSQM version 1.4 will be analyzed using a repeated measures mixed effects model, including baseline TSQM overall satisfaction scale score, visit, the prevailing erenumab dose from Week 12 onwards, and baseline MMD based on observed data. The mean change from baseline in TSQM overall satisfaction scale score at week 24 will be estimated from the least-squares mean (LSM) of the mixed effects model, and the corresponding 95% CI will be provided. The nominal p-value will be reported by comparing the mean change

Endpoint	Primary Summary and Analysis Method
	
from baseline in TSQM overall satisfaction scale score at week 24 to zero with a two-sided 5% significance level.
 
3. The efficacy analysis set will be used for this endpoint analysis.

Table 9-2. Secondary Efficacy Endpoint Summary Table

Endpoint	Primary Summary and Analysis Method
Achievement of overall satisfaction at week 24 as defined by subject reporting of satisfied, very satisfied, or extremely satisfied on Item 14 of the TSQM version 1.4	
1. Summary statistics using observed data (after intercurrent event handling);
 
2. The achievement of overall satisfaction at week 24 as defined by subject reporting of satisfied, very satisfied, or extremely satisfied on Item 14 of the TSQM version 1.4 will be analyzed using a generalized linear mixed effects model with the logit link function. The model will include baseline achievement of overall satisfaction, visit, the prevailing erenumab dose from Week 12 onwards, and baseline MMD based on observed data. The proportions and the corresponding 95% CI at week 24 will be estimated from the LSM (with inverse link function) of the mixed effects model.
 
3. The efficacy analysis set will be used for this endpoint analysis.

Improvement in subject global impression at week 24 , as defined by subject reporting of much improved or a little improved on the mGI-I	
1. Summary statistics using observed data (after intercurrent event handling);
 
2. The Improvement in global impression at week 24, as defined by subject's, clinician's, and key family member's reporting of much improved or a little

Endpoint	Primary Summary and Analysis Method

defined by treating clinician's reporting of much improved or a little improved on the mGI-I
 
Improvement in key family member's global impression at week 24, as defined by key family member's reporting of much improved or a little improved on the mGI-I
	
improved on the migraine Global Impression Item (mGI-I) will be analyzed separately using a generalized linear mixed effects model with the logit link function. The model will include the visit, the prevailing erenumab dose from Week 12 onwards, and baseline MMD based on observed data. The proportions and the corresponding 95% CI at week 24 will be estimated from the LSM (with inverse link function) of the mixed effects model.
 
3. The efficacy analysis set will be used for this endpoint analysis.


Change from baseline in subject functional impairment domain score at week 24, as measured by the Migraine Functional Impact Questionnaire (MFIQ)
 
 – Physical function domain score – Usual activities domain score – Emotional function domain score – Social function domain score 	
1. Summary statistics using observed data (after intercurrent event handling);
 
2. The change from baseline in subject functional impairment domain score at week 24, as measured by the MFIQ will be analyzed using a generalized linear mixed effects model with the identity link function. The model will include baseline subject functional impairment domain score, visit, the prevailing erenumab dose from Week 12 onwards, and baseline MMD based on observed data. The mean change from baseline in subject functional impairment domain score at week 24 with the corresponding 95% CI will be estimated from the LSM of the mixed effects model, and p-values comparing with zero at a two-sided 5% significance level will be reported.

Endpoint	Primary Summary and Analysis Method
	
3. The efficacy analysis set will be used for this endpoint analysis.
 
4. This endpoint will be analyzed separately for each functional domain.

Table 9-3. Exploratory Efficacy Endpoint Summary Table

Endpoint	Primary Summary and Analysis Method
Change from baseline in TSQM overall satisfaction scale score at weeks 12, 16, and 20 and mean over weeks 16, 20, and 24	This endpoint will be analyzed same as primary efficacy endpoint.
Achievement of overall satisfaction as defined by subject reporting of satisfied, very satisfied, or extremely satisfied on item 14 of the TSQM version 1.4 at weeks 12, 16, and 20.	This endpoint will be analyzed same as primary efficacy endpoint.
Change from baseline in TSQM sub-scale domain scores at weeks 12, 16, 20 and 24 and mean over weeks 16, 20, and 24: – effectiveness – side effects – convenience	This endpoint will be analyzed same as primary efficacy endpoint. Note: Use baseline value covariate as a “Baseline TSQM sub-scale domain score”
Improvement in subject global impression at weeks 12, 16, and 20, as defined by subject reporting of much improved or a little improved on the mGI-I Improvement in treating clinician's global impression at weeks 12, 16, and 20, as defined by treating	This endpoint will be analyzed same as above mentioned mGI-I endpoint.

Endpoint	Primary Summary and Analysis Method

clinician's reporting of much improved or a little improved on the mGI-I
 
Improvement in key family member's global impression at weeks 12, 16, and 20, as defined by key family member's reporting of much improved or a little improved on the mGI-I
	

Change from baseline in MFIQ functional impairment domain scores, at weeks 12, 16, and 20, and mean over weeks 16, 20, and 24:
 
 – Impact on physical function – Impact on usual activities – Impact on emotional function – Impact on social function 	
 1. Summary statistics by visit using observed data at each visit, and the calculated mean MFIQ physical function impairment domain score over weeks 16, 20, and 24. 2. The change from baseline in physical function impairment domain score at weeks 12, 16, and 20, and mean over weeks 16, 20, and 24, as measured by the MFIQ will be analyzed using a generalized linear mixed effects model with the identity link function. The model will include baseline MFIQ physical function domain score, visit, the prevailing erenumab dose from Week 12 onwards, and baseline MMD based on observed data. The mean change from baseline in physical function impairment domain score at weeks 12, 16, and 20, and mean over weeks 16, 20, and 24 with the corresponding 95% CI will be estimated from the LSM of the mixed effects model. 3. The efficacy analysis set will be used for this endpoint analysis.

Endpoint	Primary Summary and Analysis Method
Achievement of at least a 50% reduction from baseline in mean MMD over weeks 16, 20, and 24	
 1. Summary statistics by visit using observed data at each visit, and at least a 50% reduction from baseline in mean MMD over weeks 16, 20, and 24. 2. The achievement of at least a 50% reduction from baseline in mean MMD over weeks 16, 20, and 24 will be analyzed using a generalized linear mixed effects model with the logit link function. The model will include the prevailing erenumab dose from Week 12 onwards, and baseline MMD. The probabilities and the corresponding 95% CI for 50% reduction from baseline MMD in mean MMD over months 4 to 6 will be estimated using the mixed effects model. 3. The efficacy analysis set will be used for this endpoint analysis.
Achievement of at least a 50% reduction from baseline in MMD at weeks 16, 20, and 24	
 ○ Summary statistics by visit using observed data at each visit, and at least a 50% reduction from baseline in MMD at weeks 16, 20, and 24. ○ The change from Achievement of at least a 50% reduction from baseline in MMD at weeks 16, 20, and 24 will be analyzed using a generalized linear mixed effects model with the logit link function. The model will include achievement of at least a 50% reduction from baseline in MMD, visit, the prevailing erenumab dose from Week 12 onwards, and baseline MMD.

Endpoint	Primary Summary and Analysis Method
	
The probabilities and the corresponding 95% CI for at least 50% reduction from baseline MMD at weeks 16, 20, and 24 will be estimated using the mixed effects model.
 
 ○ The efficacy analysis set will be used for this endpoint analysis.

The same analysis methods will be applied to the below exploratory endpoints:

Change from baseline in the Migraine Symptom Severity Scale (MSSS) total score at weeks 12, 16, 20, and 24 and mean over weeks 16, 20, and 24

Change from baseline in the Migraine Interictal Burden Scale (MIBS-4) total score at weeks 12, 16, 20, and 24 and mean over weeks 16, 20, and 24

Change from baseline in mean MMD over weeks 16, 20, and 24

Change from baseline in MMD at weeks 16, 20, and 24

Change from baseline in mean monthly acute migraine-specific medication days over weeks 16, 20, and 24

Change from baseline in monthly acute migraine-specific medication days at weeks 16, 20, and 24

Change from baseline in General Anxiety Disorder scale (GAD-7) total score at weeks 12 and 24

Change from baseline in Patient Health Questionnaire (PHQ-9) total score at weeks 12 and 24

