Secondary	
In the event of IP discontinuation due to lack of efficacy or adverse event, the binary secondary endpoint after IP discontinuation will be classified as not achieving overall satisfaction or global impression on improvement; and the continuous MFIQ domain scores after treatment discontinuation will be defined as the worst postbaseline value observed before treatment discontinuation. Data collected after IP discontinuation due to other reasons will be censored and not included in the analysis.
 
A generalized linear mixed effects model with the appropriate link function will be used to analyze each secondary endpoint based on observed data. The model will include the corresponding baseline value for the endpoint being analyzed (except for the global impression endpoints), visit, the prevailing erenumab dose from week 12 onwards, and baseline MMD.
 
For binary secondary endpoints, logit link function will be used, and the proportions and the corresponding 95% CI at week 24 will be estimated from the LSM (with inverse link function) of the mixed effects model.
 
For the continuous MFIQ domain score endpoints, identity link function will be used, and mean change from baseline in each domain score at week 24 with the corresponding 95% CI will be estimated from the LSM of the mixed effects model, and p-values comparing with zero at a 2-sided 5% significance level will be reported.

Exploratory	Will be described in the statistical analysis plan (SAP) finalized before database lock

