The primary estimand for the primary efficacy objective is the mean change from baseline in TSQM overall satisfaction scale score at week 24 in subjects with EM or CM who are currently on 1 standard of care migraine prevention therapy and who receive at least 1 dose of IP and have a baseline and at least 1 post-baseline TSQM overall satisfaction scale score, and a composite strategy will be used for subjects who discontinued IP due to lack of efficacy or adverse event with data after IP discontinuation defined by the worst postbaseline value observed up to IP discontinuation (inclusive), while a hypothetical strategy will be used for those subjects who discontinued IP due to other reasons with data collected after IP discontinuation censored.

Secondary

• To assess the effect of erenumab on medication-specific treatment satisfaction	
• Achievement of overall satisfaction at week 24 as defined by subject reporting of satisfied, very satisfied, or extremely satisfied on Item 14 of the TSQM version 1.4
--	--

The estimand for the secondary efficacy objective on treatment satisfaction consists of:

- The target population, which includes subjects with EM or CM currently on 1 standard of care migraine prevention therapy
- The endpoint, which is achievement of overall satisfaction at week 24 as defined by subject reporting of satisfied, very satisfied, or extremely satisfied on Item 14 of the TSQM

- There are 2 intercurrent events, discontinuation of IP due to lack of efficacy or adverse event, and discontinuation of IP due to other reasons. The treatment effect of interest will be assessed for all subjects who receive at least 1 dose of IP and have a baseline value and at least 1 post-baseline value for Item 14 of the TSQM. A composite strategy will be used for subjects who discontinued IP due to lack of efficacy or adverse event where they will be defined as not satisfied after IP discontinuation. A hypothetical strategy will be used for those subjects who discontinued IP due to other reasons with data collected after IP discontinuation censored.
- The treatment, which is erenumab 70 or 140 mg every 4 weeks
- The summary measure, which is the proportion of subjects who achieves overall satisfaction at week 24

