
The estimand for the secondary efficacy objectives on impression of change in migraine consists of:
 
• The target population, which includes subjects with EM or CM currently on 1 standard of care migraine prevention therapy• The endpoints, which include:
• Improvement in subject global impression at week 24, as defined by subject reporting of much improved or a little improved on the mGI-I• Improvement in treating clinician's global impression at week 24, as defined by the clinician's reporting of much improved or a little improved on the mGI-I for each individual subject• Improvement in key family member's global impression at week 24, as defined by family member's reporting of much improved or a little improved on the mGI-I for each individual subject• There are 2 intercurrent events, discontinuation of IP due to lack of efficacy or adverse event, and discontinuation of IP due to other reasons. The treatment effect of interest will be assessed for all subjects who receive at least 1 dose of IP and have at least 1 post-baseline value of each respective mGI-I item. A composite strategy will be used for subjects who discontinued IP due to lack of efficacy or adverse event where they will be defined as not improved after IP discontinuation. A hypothetical strategy will be used for those subjects who discontinued IP due to other reasons with data collected after IP discontinuation censored.• The treatment, which is erenumab 70 or 140 mg every 4 weeks	

- The summary measure, which is the proportion of subjects who achieves impression of improvement at week 24.

The estimand for the secondary efficacy objective on impression of change in migraine is the proportion of subjects who achieves global impression of migraine improvement at week 24 as defined by subject, treating clinician, or family member reporting of much improved or a little improved on the mGI-I, in subjects with EM or CM who are currently on 1 standard of care migraine prevention therapy and who receive at least 1 dose of IP and have at least 1 post-baseline value of the respective mGI-I, and a composite strategy will be used for subjects who discontinued IP due to lack of efficacy or adverse event where they will be defined as not improved after IP discontinuation, while a hypothetical strategy will be used for those subjects who discontinued IP due to other reasons with data collected after IP discontinuation censored.

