8.7 Validation of Statistical Analyses

Programs will be developed and maintained, and output will be verified in accordance with current risk-based quality control procedures.

Tables, figures, and listings will be produced with validated standard macro programs where standard macros can produce the specified outputs.

The production environment for statistical analyses consists of Amgen-supported versions of statistical analysis software; for example, the SAS System version 9.4 or later.

9. Statistical Methods of Analysis

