9.5.2 Analyses of Secondary Efficacy Endpoint(s)

The secondary efficacy endpoints calculated by the methods as specified detailed in [Table 9-2](#). Secondary Efficacy Endpoint Summary Table, column Primary Summary and Analysis Method.

For continuous secondary endpoints, a generalized linear mixed effects model with the identity link function will be used. The model will include the corresponding baseline value for the endpoint being analyzed, visit, the prevailing erenumab dose from Week 12 onwards, and baseline MMD. The corresponding 95% CI will be estimated from the LSM of the mixed effects model, and p-values comparing with zero at a two-sided 5% significance level will be reported.

For binary secondary endpoints, a generalized linear mixed effects model with the logit link function will be used. The model will include the corresponding baseline value for the endpoint being analyzed (except for the global impression endpoints), visit, the prevailing erenumab dose from Week 12 onwards, and baseline MMD. The proportions and the corresponding 95% CI will be estimated from the LSM (with inverse link function) of the mixed effects model and will be reported.

The secondary endpoints will be analyzed in the following subgroups:

- Whether remained on standard of care migraine preventive treatment throughout the study (yes vs. no)
- Migraine type (EM vs. CM)

The subgroups will be re-examined for appropriateness and may be re-categorized (due to small sample size, for example, if there are < 10% of subjects within a subgroup) before final analysis.

The purpose of the subgroup analyses is to explore if the treatment effect varies across subgroups of interest. Subgroup analyses will be performed using the same method as primary analysis method but within level of each subgroup of interest.

The efficacy analysis set will be used for this endpoints analyses.

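### Binary secondary endpoints: the back-transformed logit mixed-model LS-mean need not be the proportion of subjects named in the estimand, and it carries the only specified 95% CI

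*SAP*

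**What the plan says.** The estimands in SAP 2.1 are population proportions. For Item 14: "The summary measure, which is the proportion of subjects who achieves overall satisfaction at week 24". For the three mGI-I endpoints: "The summary measure, which is the proportion of subjects who achieves impression of improvement at week 24".

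The estimator is given three times and is always the same. SAP Table 9-2 says: "The proportions and the corresponding 95% CI at week 24 will be estimated from the LSM (with inverse link function) of the mixed effects model". SAP 9.5.2 repeats that the proportions and CI "will be estimated from the LSM (with inverse link function) of the mixed effects model and will be reported", and Protocol 9.4.2.2 has the same rule: "will be estimated from the LSM (with inverse link function) of the mixed effects model".

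The model description stops at fixed effects. For Item 14: "The model will include baseline achievement of overall satisfaction, visit, the prevailing erenumab dose from Week 12 onwards, and baseline MMD". The mGI-I models have the same terms without a baseline value. Neither document states a random effect, a within-subject covariance structure, an estimation method, the coding of dose or baseline satisfaction, or the LS-mean weights. SAP 8.7 names software ("for example, the SAS System version 9.4 or later") but no procedure.

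Table 9-2 also lists observed-data summaries after intercurrent-event handling. SAP 9.1 defines these, for categorical endpoints, as number and percentage, without a CI.

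**The concern.** The logit link is non-linear, so the inverse link of an average logit is not the average of the probabilities. In a model with a subject random intercept, the inverse link of the LS-mean describes a subject at the centre of the random-effect distribution. The estimand asks what fraction of all subjects are satisfied or improved. The two agree at 50% and separate on either side, with the model value always the more extreme.

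This study has no comparator, so no between-arm contrast can absorb the shift. The proportions and their intervals are the secondary results, and SAP 3.2 says that their precision drove the sample size. If the true proportion is above 50%, the shift is in the favourable direction, and an interval centred on the wrong quantity covers the estimand less often than 95%.

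**Working it through.** **1. The plan's own figures.** Half-width = 1.96 × √(p(1−p)/n). With n = 216 (240 × 0.9) and p = 0.70: 1.96 × √(0.21/216) = 6.11 points. At 50 / 60 / 80% it gives 6.67 / 6.53 / 5.33. With n = 289 it gives 5.77 / 5.65 / 5.28 / 4.61 at 50 / 60 / 70 / 80%. All eight entries of SAP Tables 3-1 and 3-2 reproduce to one decimal. The planned precision is therefore that of a simple proportion of subjects.

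**2. Size of the gap under a random intercept.** Let η be the week-24 LS-mean on the logit scale and σ the random-intercept SD. The proportion of subjects is p = E[expit(η + σZ)] with Z standard normal. The SAP would report expit(η). I solved for η at a given p by Gauss-Hermite quadrature. The documents give no σ, so 0.5 to 2 is an assumed range.

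| σ | Between-visit correlation of the yes/no response at 70% | True 70%: η, reported value (gap) | True 80%: η, reported value (gap) |
|---|---|---|---|
| 0.5 | 0.05 | 0.895, 71.0% (+1.0) | 1.459, 81.1% (+1.1) |
| 1 | 0.16 | 1.018, 73.5% (+3.5) | 1.650, 83.9% (+3.9) |
| 1.5 | 0.27 | 1.188, 76.6% (+6.6) | 1.916, 87.2% (+7.2) |
| 2 | 0.38 | 1.384, 80.0% (+10.0) | 2.228, 90.3% (+10.3) |

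At a true 60% the gaps are +0.6 / +2.0 / +3.9 / +6.1; at 50% they are zero. The gap reaches the Table 3-2 half-width at σ of about 2.1 (60%), 1.4 (70%) and 1.2 (80%).

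**3. Dependence on the fit.** Simulation: 240 subjects, four visits with equal true proportion, assumed dropout per interval of 1.5% after a response and 8.5% after a non-response, 500 trials per setting. Results are for σ = 1 / 1.5 / 2.

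| Fit and summary | Mean at true 70% | Coverage of 70% | Mean at true 80% | Coverage of 80% |
|---|---|---|---|---|
| Maximum likelihood, inverse link | 73.3 / 76.6 / 79.9% | 83 / 61 / 40% | 83.9 / 87.1 / 90.4% | 78 / 40 / 10% |
| Linearised (pseudo-likelihood), inverse link | 70.9 / 72.1 / 73.5% | 95 / 92 / 88% | 80.8 / 82.0 / 83.5% | 95 / 91 / 80% |
| Marginal, exchangeable correlation, robust SE | 70.0% | 94 to 95% | 80.0 to 80.1% | 94 to 95% |
| Maximum likelihood, averaged over the random effect | 70.0% | 95 to 96% | 79.9 to 80.1% | 95 to 96% |

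Monte Carlo error is at most 2.2 points for coverage. The last row had mean half-widths of 6.1 and 5.3, equal to Table 3-2. A separate simulation (216 subjects, complete data, 300 runs, true 70%) gave maximum-likelihood inverse-link coverage of 82% at σ = 1 and 44% at σ = 2, with half-widths of about 7.3 and 8.3.

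**4. Two side checks.** Averaging over the random effect after a linearised fit over-corrects, because that fit underestimates σ (mean 0.77 / 1.07 / 1.32 for true 1 / 1.5 / 2): it gave 68.8 / 68.5 / 68.4% at a true 70%. Under any of the fits, evaluating at mean covariates instead of averaging over subjects adds 0.3 or 1.0 point at 70% if the covariate part of the logit has an assumed SD of 0.25 or 0.5.

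**The case against.** A reader might infer that the reported proportions will certainly be inflated by several points and that their intervals will certainly under-cover. The documents do not support that:

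- **Structure.** No random effect is stated. SAP Table 9-3 uses the same label for response based on mean MMD, an endpoint with one value per subject and no visit term: it says the endpoint "over weeks 16, 20, and 24 will be analyzed using a generalized linear mixed effects model with the logit link function". A subject random effect there has no repeated records to be estimated from, so the label alone does not fix the structure. The primary analysis is a repeated-measures model, so a residual-side fit is a live reading, and under it coverage was 94 to 95%.
- **Size.** The SD, the response rates and the simulated dropout are all assumed. At an SD of 0.5 the gap is about one point. The simulations also leave out the rule that turns values after discontinuation for lack of efficacy or adverse event into non-response. That rule creates runs of identical values within a subject, which argues against a negligible SD but does not supply one.
- **Direction.** Tables 3-1 and 3-2 start at 50%, where there is no gap. Below 50% the shift would be unfavourable.
- **Visibility.** The observed percentage is an item in the same Table 9-2 cell, so a divergence would show. The study is descriptive, with no hypothesis or decision rule.

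A reader might also infer a further bias in the Item 14 result from equally weighted LS-means. The documents give neither the coding nor the association of baseline satisfaction with outcome, so no size can be put on it.

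These points limit the size and certainty of the shift. They do not remove the mismatch: the stated rule attaches the only specified CI to a quantity that, under the ordinary random-intercept reading of a mixed model, is not the estimand.

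**Conclusion.** The point holds conditionally and should be fixed. With a subject random intercept, the specified estimator misses the estimand at any proportion other than 50%. Under maximum likelihood the miss runs from about 1 point (SD 0.5) to about 10 points (SD 2) at true proportions of 70 to 80%, so within the assumed range it can exceed the planned half-width. With a linearised fit and SDs of 1 to 2 it is about 1 to 3.5 points. With residual-side correlation only, the random-effect part is absent and at most a small covariate-averaging difference remains. The SAP wording is compatible with all three, so the meaning of the headline percentages and the true coverage of their intervals depend on an unstated programming choice. Naming the structure alone would not be enough, because a clearly stated random-intercept model would still report the wrong quantity.

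**What to change.** In SAP Table 9-2 and 9.5.2, define the reported week-24 proportion and its 95% CI as marginal, and state the route:

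- **(a)** Fit a random-intercept logistic model by maximum likelihood (quadrature). Average the fitted week-24 probabilities over the random-effect distribution and over the analysed subjects' own dose, baseline and MMD values. Use a delta-method or bootstrap CI.
- **(b)** Or fit a marginal model (residual-side or GEE) with its working correlation stated, and average the fitted probabilities over the subjects' own covariate values, with a matching CI.

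Do not average over the random effect after a linearised fit. Averaging over the subjects' own covariates also settles the coding and LS-mean weight questions.

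Cost: SAP wording, a few more lines of code and no new data. The reported proportions may be somewhat less extreme than the back-transformed LS-means.
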